9.2.3 Additional Analyses

The primary analysis will be repeated for:

• the selected arm only, i.e. comparing all patients on the selected arm (from part 1) from both parts of the trial (pooled), to all patients on the placebo arm from both parts of the trial.

Page 29 of 80

• data from part 2 only, i.e. comparing the selected arm to placebo on data from part 2 only

9.3 Secondary Endpoints

For the purpose of a possible label inclusion, the Hochberg procedure (4) for adjustment on multiplicity will be implemented to selected key secondary endpoints. Only if the primary efficacy analysis leads to a statistically significant result at the (one-sided) 2.5% level, then the Hochberg procedure which is described below is applied to selected key secondary analyses. If the primary efficacy analysis does not result in statistical significance at the (one-sided) 2.5% level, then statistical significance (for the purpose of a possible label inclusion only) will not be declared for any of the key secondary analyses, regardless of their p-values.

The selected key secondary endpoints aimed at further demonstrating treatment effect are:

- All-cause mortality (defined as the fraction of patients that have died, regardless of cause, by the end of Day 90)
- Renal replacement therapy-free days up to Day 30 (excluding patients on RRT for chronic renal failure at time of randomisation)
- ICU-free days up to Day 30

In this application of the Hochberg procedure there are three hypothesis tests of superiority for each of the selected secondary endpoints. The target alpha level is (one-sided) 2.5%. The Hochberg procedure is as follows:

- Order the p-values from the smallest to the largest value, p(1) < p(2) < p(3), with corresponding null hypothesis $H_{(1)}$, $H_{(2)}$, and $H_{(3)}$.
- Start with the highest p-value. If p(3) < 2.5% (one-sided), then stop and declare all three comparisons significant at the 2.5% (one-sided) level (i.e. reject H₍₁₎, H₍₂₎, and H₍₃₎). Otherwise, accept H₍₃₎ for the endpoint related to p(3), and go to p(2) the second highest p-value.
- If p(2) < 2.5/2 = 1.25% (one-sided), then stop and declare significance for $H_{(1)}$ and $H_{(2)}$. Otherwise, accept $H_{(2)}$, for the endpoint related to p(2), and go to p(1) the lowest p-value.
- If p(1) < 2.5/3 = 0.833% (one-sided), then stop and declare significance for $H_{(1)}$. Otherwise, accept $H_{(1)}$, for the endpoint related to p(1).

Regardless of the statistical significance declared according to the Hochberg procedure, all analysis will be included and presented in the statistical report.

As for the primary analysis, the primary comparison (which determines the success, i.e. statistical and clinical significance) for the secondary efficacy endpoints is between all patients on all selepressin arms from both parts of the trial (pooled together and treated as a single arm) and all patients on the placebo arm from both parts of the trial.

Date: 20 Nov 2017 E-Statistical Analysis Plan-17877; Ver.9.0 Supersedes: Ver. 8.0

Page 30 of 80

As an additional analysis, all secondary efficacy analyses will, as for the primary, be repeated for:

- the selected arm only, i.e. comparing all patients on the selected arm (from part 1) from both parts of the trial (pooled), to all patients on the placebo arm from both parts of the trial.
- data from part 2 only, i.e. comparing the selected arm to placebo on data from part 2 only

All free-days endpoints will be reported to one decimal place.

9.3.1 Organ Dysfunction

9.3.1.1 Vasopressor-free Days up to Day 30

Vasopressor-free Days up to Day 30 will be defined and analyzed in a similar manner as the primary endpoint, with the van Elteren test stratified by need for ventilation (Yes/No), time from onset of shock to start of treatment (< or \ge 6 hours), and norepinephrine/noradrenaline requirement at baseline (< or \ge 30 µg/min).

9.3.1.2 Mechanical Ventilator-free Days up to Day 30

Ventilator -free Days up to Day 30 will be defined and analyzed in a similar manner as the primary endpoint, with the van Elteren test stratified by need for ventilation (Yes/No), time from onset of shock to start of treatment (< or \ge 6 hours), and norepinephrine/noradrenaline requirement at baseline (< or \ge 30 µg/min).

9.3.1.3 Duration of Septic Shock up to Day 30

Duration of septic shock is defined as the cumulative periods (>1 hour) from start of IMP until Day 30, on IMP or vasopressors. Vasopressor use due to anaesthesia / procedure-induced hypotension during - and up to three hours after - surgery / procedure (including bedside) is exempt from this rule

For patients withdrawn (in the survivors analysis) or dying (in the non-survivors analysis) while still in septic shock, the duration will be based on the data available up until the time of withdrawal or death.

Duration of septic shock will be analyzed separately for survivors, non-survivors (within the first 30 days) and overall, comparing treatment arms by a negative binomial model with time from onset of shock to start of treatment and norepinephrine/noradrenaline requirement at baseline (µg/kg/min) as covariates, and treatment and need for ventilation (Yes/No) as factors. The estimated treatment difference (to placebo) with a 95% confidence interval will be presented. As duration of septic shock is derived with two decimal points (with values in the range of 0.00, 0.01, ..., 30.00), duration of septic shock MAY be transformed (for model stability) to integer values (with values in the range of 0, 1, ..., 3000) by multiplying with 100. Treatment estimates will be back transformed

Date: 20 Nov 2017 E-Statistical Analysis Plan-17877; Ver.9.0 Supersedes: Ver. 8.0 Page 31 of 80

Some patients will get out of shock prior to Day 30 (and stay alive until Day 30), some will get out of shock and die later on (prior to Day 30), others will die or be withdrawn while still in shock (prior to Day 30), and the remaining few will not get out of shock prior to Day 30. This means that if mortality and withdrawal rates vary between treatment arms, the results of the analysis for the overall population will be influenced by the skewed mortality and withdrawal rates. Hence, for the overall population, the distribution of duration of shock (time to out of shock), will be presented graphically as competing risks between 'time to out of shock', 'withdrawn while in shock' and 'dying while in shock'. Further, Kaplan-Meier (sub)-graphs on 'time to death' and 'time to withdrawal' will be presented for those getting out of shock (for which some will die or be withdrawn later on, prior to Day 30). This is done in order to elucidate any skewness in mortality and withdrawal rates, influencing the results of the analysis.

Furthermore, duration of septic shock will be tabulated by treatment arm (including pooled active treatment arms).

In case the model assumptions does not hold, covariates will be dichotomised (in same manner as they have been dichotomised for other endpoint analyses) and duration of septic shock will be analysed using a stratified permutation test (Monte Carlo estimate of p-value). Treatment effects (and treatment difference) will be the raw (unadjusted/non-stratified) means. The confidence intervals for the individual treatment arms will be derived by bootstrapping 5000 samples (within treatment group) with same number of observations (within treatment group), and taking the 2.5 and 97.5% percentiles from the distribution of the 5000 means from the bootstrapped samples. The confidence interval for the treatment difference will be derived via significance testing (based on the stratified permutation test), i.e. the confidence interval will be constructed by including the 95% confidence region for all those values for which the significance test of the hypothesis that the true value is the given value is not rejected at a 5% significance level (e.g. if we test is treatment difference=1 and p-value >0.05 then we include 1 in the confidence interval, and so on). The seed for both the Monte Carlo derived p-value and the bootstrapped confidence intervals will (appropriately) be seed=133.

9.3.1.4 Duration of Mechanical Ventilation up to Day 30

Duration of mechanical ventilation is defined as the cumulative periods (>1 hour) from start of IMP until Day 30, on mechanical ventilation. Mechanical ventilation during - and up to three hours after - surgery / procedure is exempt from this rule.

For patients withdrawn or dying while still on mechanical ventilation, the duration will be based on the data available up until the time of withdrawal or death.

Duration of mechanical ventilation will be analyzed separately for survivors, non-survivors (within the first 30 days) and overall using a zero inflated negative binomial model with time from onset of shock to start of treatment, and norepinephrine/noradrenaline requirement at baseline (μ g/kg/min) as covariates, and treatment and need for ventilation as factors. As duration of ventilation is derived with two decimal points (with values in the range of 0.00, 0.01, ..., 90.00), duration of ventilation

Page 32 of 80

will be transformed (for model stability) to integer values (with values in the range of 0, 1, ..., 9000) by multiplying with 100. Treatment estimates will be back transformed.

In case the model assumptions for duration of ventilation does not hold, the permutation test specified in Section 9.3.1.3 will be used including an analysis of the expected proportion of patients with 0 duration, and estimates of the duration for those with a positive duration.

9.3.1.5 Daily Overall and Individual Organ (Cardiovascular, Respiratory, Renal, Hepatic, Coagulation) Scores using the Modified Sequential Organ Failure Assessment (SOFA) Scores Until ICU Discharge

Last observation carried forward (LOCF) will be used for missing SOFA scores on Days 2-7. No LOCF for Day 1 (as previous value is baseline). Patients dying will be imputed with a worst possible outcome, i.e. a value of 4 for each individual SOFA score.

Daily overall (modified) and individual SOFA scores will be compared between treatment arms up until Day 7 using a repeated measures ANCOVA model with baseline SOFA score as covariate, treatment, time and treatment by time interaction as factors, baseline SOFA score by time interaction, and patient as the experimental unit. The estimated treatment difference (to placebo) with a 95% confidence interval will be presented.

Furthermore, daily overall and individual SOFA scores will be tabulated by treatment arm (including pooled active treatment arms).

9.3.1.6 Incidence of New Organ Dysfunctions and New Organ Failures (Based on the SOFA score) up to Days 7 and 30

Incidence of new organ failures is defined as a change in any of the individual SOFA scores from (0,1,2) at baseline to (3,4) post baseline up until the end of the period (Day 7 or 30) (if the SOFA scores goes from (0,1,2) to (3,4) and back to (0,1,2) again within the period, that will still count as a new organ failure). If a patient dies within the period, he is considered to fail on all organs, and the number of new organ failures will be all organs except those already failed at baseline. Patients withdrawn within the period will be evaluated based on the data available at time of withdrawal.

Incidence of new organ dysfunction is defined as an increase ≥ 1 from baseline to post baseline up until the end of the period (e.g. going from 1 to 2) in any of the individual SOFA scores. Patients with an individual SOFA score of 4 at baseline can per default not have a new organ dysfunction. If a patient dies within the period, he is considered to have dysfunction on all organs, and the number of new organ dysfunctions will be all organs except those already having a score of 4 at baseline. Patients withdrawn within the period will be evaluated based on the data available at time of withdrawal.

As the SOFA score is only collected for patients still in the ICU, it is assumed that as soon as the patient leaves the ICU, the patient will not experience any new organ dysfunctions or organ failures. Unless of course the patient dies.

Date: 20 Nov 2017 E-Statistical Analysis Plan-17877; Ver.9.0 Supersedes: Ver. 8.0

Page 33 of 80

Incidence of at least one new organ failure will be analyzed for any new organ failure (across all organ systems) and by individual organ systems, and compared between treatment arms using a logistic regression model with age, modified SOFA score and norepinephrine/noradrenaline requirement at baseline ($\mu g/kg/min$) as covariates and gender and treatment arm as factors, presenting odds ratios with 95% confidence intervals.

Incidence of at least one new organ dysfunction will be analyzed for any new organ dysfunction (across all organ systems) and by individual organ systems, and will be analyzed as above for new organ failures.

The number of new organ failures and the number of new organ dysfunctions will be compared between treatment arms using a negative binomial model with age, modified SOFA score and norepinephrine/noradrenaline requirement at baseline ($\mu g/kg/min$) as covariates, and gender and treatment as factors. The estimated treatment difference (to placebo) with a 95% confidence interval will be presented. The 95% confidence interval for the difference in proportions between treatment groups will be constructed using the delta method (see Appendix 4 for details).

Furthermore, incidence of any new organ failure and any new organ dysfunction, and the number of new organ failures and new organ dysfunctions will be tabulated by treatment arm (including pooled active treatment arms).

9.3.1.7 Renal Replacement Therapy (RRT)-free Days up to Day 30 (excluding patients on RRT for chronic renal failure at time of randomisation)

RRT-free Days is defined as for the primary endpoint with free of treatment with any form of renal replacement therapy defined as continuous renal replacement therapy, intermittent hemodialysis or peritoneal dialysis.

RRT-free Days will be analyzed excluding patients on RRT for chronic renal failure at time of randomisation.

RRT-free Days up to Day 30 will be analyzed in a similar manner as the primary endpoint, with the van Elteren test stratified by need for ventilation (Yes/No), time from onset of shock to start of treatment (< or \ge 6 hours), norepinephrine/noradrenaline requirement at baseline (< or \ge 30 μ g/min) and baseline creatinine (< or \ge 150 μ mol/L).

9.3.1.8 Incidence of RRT up to Day 30 (counting patients who die as on RRT and excluding patients on RRT for chronic renal failure at time of randomisation)

RRT is defined as any form of renal replacement therapy defined as continuous renal replacement therapy, intermittent hemodialysis or peritoneal dialysis. In order to ensure that any reduction in incidence of RRT is not caused by an increase in mortality, all patients dying within the 30-day period will be counted as on RRT. For patients withdrawn prior to Day 30, incidence of RRT will be based on the data available up until the time of withdrawal.

Page 34 of 80

Incidence of RRT will be analysed by a logistic regression model with time from onset of shock to start of treatment, baseline creatinine and norepinephrine/noradrenaline requirement at baseline (µg/kg/min) as covariates, and treatment and need for ventilation as factors. The 95% confidence interval for the difference in proportions between treatment groups will be constructed using the delta method (see Appendix 4 for details). Patients already on RRT for chronic renal failure at time of inclusion will be excluded from the analysis of incidence of RRT.

Non-inferiority will be claimed if the upper limit of the two-sided 95% CI of the adjusted difference in proportions is less than 20% of the estimated incidence of RRT in the placebo group. Superiority can be claimed (5) if the upper limit is less than 0.

I.e., let $\widehat{p_S}$ and $\widehat{p_P}$ be the estimated incidences of RRT in the combined selepressin groups and the placebo group respectively. Non-inferiority will then be claimed if

$$\widehat{p_S} - \widehat{p_P} + 1.96 * \sqrt{var(\widehat{p_S} - \widehat{p_P})} < 0.2 * \widehat{p_P}$$

and superiority will be claimed if

$$\widehat{p_S} - \widehat{p_P} + 1.96 * \sqrt{var(\widehat{p_S} - \widehat{p_P})} < 0$$

A forest plot including the non-inferiority tests for all analyses will be presented.

Furthermore, incidence of RRT will be tabulated by treatment arm (including pooled active treatment arms).

A subgroup analysis will be performed on patients without acute RRT at baseline.

9.3.1.9 Duration of RRT up to Day 90 (excluding patients on RRT for chronic renal failure at time of randomisation)

Duration of RRT is defined as the cumulative periods with RRT (continuous renal replacement therapy, intermittent hemodialysis or peritoneal dialysis) and will be analyzed excluding patients on RRT for chronic renal failure at time of randomisation.

For patients withdrawn or dying while still on RRT, the duration will be based on the data available up until the time of withdrawal or death.

Duration of RRT will be analyzed as for duration of ventilation (also by transforming to integers) in Section 9.3.1.4 with time from onset of shock to start of treatment, baseline creatinine and norepinephrine/noradrenaline requirement at baseline (μ g/kg/min) as covariates, and treatment and need for ventilation as factors. The supportive competing risk and Kaplan-Meier graphs described in Section 9.3.1.4 will not be performed as it makes no sense since RRT durations are short and repetitive. It is more meaningful to just look at 90 day mortality and withdrawal rates to take eventual skewed mortality and withdrawal rates into account.

Page 35 of 80

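### Section 9.3.1.6 sets no at-risk denominator for the per-organ models, so patients whose organ had already failed at baseline enter as certain non-events, even when they die

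*SAP*

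**What the plan says.** SAP section 9.3.1.6 defines a new organ failure by the baseline state of the organ: it is "defined as a change in any of the individual SOFA scores from (0,1,2) at baseline to (3,4) post baseline". For a patient who dies, "he is considered to fail on all organs", but "the number of new organ failures will be all organs except those already failed at baseline". New dysfunction is a rise of at least one point. There a death counts for "all organs except those already having a score of 4 at baseline", and the text acknowledges the ceiling: "Patients with an individual SOFA score of 4 at baseline can per default not have a new organ dysfunction".

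The yes/no endpoint "will be analyzed for any new organ failure (across all organ systems) and by individual organ systems", by logistic regression, and dysfunction is handled the same way. The covariates are "age, modified SOFA score and norepinephrine/noradrenaline requirement at baseline", with gender and treatment arm as factors. The score of the organ under analysis is not among them.

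No at-risk subset is named for the per-organ models. Section 9.1 places all efficacy endpoints on the full analysis set.

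**The concern.** An organ at 3-4 at baseline cannot newly fail, and an organ at 4 cannot worsen. If such patients stay in that organ's model, they are certain non-events in both arms. A patient who enters with the organ failed and then dies is coded like a survivor who never developed failure in it. Adjusting for the total modified SOFA score does not identify these patients, because the same total can arise with or without this organ failed.

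At stake is how the per-organ results read. The incidence and the between-arm difference are scaled down by a share that differs from organ to organ and is not reported, so organs cannot be compared with each other. The odds ratio is also pulled towards 1.

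Elsewhere the SAP handles baseline status explicitly. Section 9.3.1.8 removes patients on chronic RRT from the RRT incidence analysis and plans a subgroup without acute RRT at baseline.

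**Working it through.** The SAP states no rate, power or sample size for this endpoint, so there is no figure to reproduce.

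**Inputs**
- Placebo mortality 25% (Appendix 8). Consistency check: 0.75 × 24 = 18.0, the overall P&VFD mean given there.
- 1800 evaluable patients (section 3.2). Arm sizes assume Part 1 = 800 with one third on placebo, and Part 2 = 1000 at 1:1: placebo 267 + 500 = 767, active 1033.
- Two-sided 5% (section 9.1).
- Assumed, not in the SAP: active mortality 30%; new-failure rate q = 5% among at-risk survivors; share f with the organ already failed at baseline, 0.1 to 0.95, independent of death and arm.

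**Formulas** (m = mortality)
- As written: (1 − f) × [m + (1 − m)q]
- At-risk patients only: m + (1 − m)q
- Power: Φ[(Δ − 1.96·SE₀)/SE₁], with SE₀ pooled and SE₁ unpooled; at-risk arm sizes are multiplied by (1 − f).

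**At f = 0.5**
- At risk: 0.25 + 0.75 × 0.05 = 0.2875 and 0.30 + 0.70 × 0.05 = 0.335. Difference 4.75 points; OR = (0.335/0.665)/(0.2875/0.7125) = 1.25.
- As written: half of each, 0.1438 and 0.1675. Difference 2.375 points; OR = (0.1675/0.8325)/(0.1438/0.8562) = 1.20.
- Risk ratio: 1.165 both ways, because (1 − f) cancels.
- Power as written: (0.02375 − 1.96 × 0.01736)/0.01719 = −0.60, giving 28%.
- Power at risk (383.5 and 516.5 patients): (0.0475 − 1.96 × 0.03131)/0.03107 = −0.45, giving 33%.

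**Range over f.** The at-risk analysis gives 28.8% vs 33.5%, 4.75 points and OR 1.25 in every row.

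| f | As written | Difference (points) | OR | Power as written | Power at risk |
|---|---|---|---|---|---|
| 0.1 | 25.9% vs 30.2% | 4.3 | 1.24 | 51% | 53% |
| 0.3 | 20.1% vs 23.5% | 3.3 | 1.22 | 39% | 43% |
| 0.5 | 14.4% vs 16.8% | 2.4 | 1.20 | 28% | 33% |
| 0.8 | 5.8% vs 6.7% | 0.95 | 1.18 | 13% | 16% |
| 0.95 | 1.4% vs 1.7% | 0.24 | 1.17 | 6% | 7% |

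With q = 20% and f = 0.5, the figures are 2.0 vs 4.0 points, OR 1.13 vs 1.18, and power 17% vs 22%.

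**Deaths affected.** At 25% of 1800 there are 450 deaths. Those coded as non-events for an organ number 450 × f: 45 at f = 0.1, 225 at 0.5, 360 at 0.8.

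**Any-organ analysis.** A death is a non-event only if all five organs had failed at baseline. With independent organs and assumed shares 1/0.5/0.3/0.1/0.1 this is 0.15% of deaths; at 1/0.7/0.4/0.2/0.2 it is 1.1%; at 0.5 each it is 3.1%. It becomes large only if nearly every organ has failed in most patients (41% at 1/0.8/0.8/0.8/0.8).

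**Comparison with section 9.3.1.5**, where "Patients dying will be imputed with a worst possible outcome, i.e. a value of 4 for each individual SOFA score". Putting that 4 into the definitions of 9.3.1.6:
- Failure: baseline 0-2 to 4 is new; baseline 3-4 to 4 is not.
- Dysfunction: baseline 0-3 to 4 is a rise; 4 to 4 is not.

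This is exactly the death rule of 9.3.1.6.

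**The case against.** The strongest reply is that the SAP never says these patients stay in the per-organ models. That follows from silence plus the full-analysis-set rule. The exception clause is worded for the number of failures, and the statement that a deceased patient fails on all organs could be read as an event in every per-organ variable. This is a fair point about certainty. It does not remove the problem, because the two readings give very different results: at f = 0.5, counting every death as an event gives 0.25 + 0.75 × 0.5 × 0.05 = 26.9% vs 0.30 + 0.70 × 0.5 × 0.05 = 31.8%, against 14.4% vs 16.8%. Surviving patients with the organ already failed remain certain non-events under either reading.

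It can also be said that the gain is modest: a few points of power, an unchanged risk ratio, and a secondary endpoint outside the Hochberg family. That stands and limits the weight of the point.

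A reader might go further and infer any of the following. The document supports none of them.
- *Excess mortality is hidden.* Death gives zero P&VFDs in the primary endpoint, Day 90 mortality is a key secondary endpoint, and mortality is modelled at Days 30, 90 and 180.
- *Sections 9.3.1.5 and 9.3.1.6 contradict each other.* One measures level and the other new events; the death rules agree, as shown above.
- *Death is rewarded.* A patient with five failed organs who dies scores zero new failures, but would also score zero if alive. For any baseline state, a death scores at least as many new failures as survival.
- *The count model needs every death scored as five.* That would call already failed organs new and change the estimand. As written, a death still adds 2.5 to 3 new failures on average at the first three sets of assumed shares in the any-organ check.

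**Conclusion.** The point holds for the per-organ logistic models only. With no at-risk denominator stated, patients who cannot have the event enter as non-events, including when they die. The risk difference is multiplied by (1 − f), the odds ratio is attenuated (1.25 to 1.20 at f = 0.5, to 1.18 at f = 0.8), and a little power is lost (33% to 28%, and 16% to 13%).

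These sizes are illustrations. They rest on the assumed f, q and 30% active mortality, on baseline failure being independent of death and arm, on unadjusted proportions, and on the planned 1800 patients, although the SAP records that the trial stopped for futility. The SAP gives neither baseline failure rates nor the modified SOFA cut-offs, so whether many or few deaths are affected cannot be settled from it. The any-organ and count analyses need no change.

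**What to change.** In section 9.3.1.6:
- restrict each per-organ logistic model to patients at risk in that organ at baseline (score 0-2 for new failure, 0-3 for new dysfunction);
- state that every death within the period in that set counts as an event;
- report the number at risk per arm for each organ.

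The cost is a few sentences and one filter per model. N per organ becomes smaller, but the patients removed could not have contributed an event. If nearly all patients have an organ failed at baseline, few remain (at f = 0.95, about 38 placebo and 52 active), and the reported number at risk will show it.

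Deaths of patients not at risk in an organ then leave that organ's model and are not recovered there. If excess deaths fell only among them, the restricted model would not show them any more than the present one does. The mortality analyses remain the place for those deaths.

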9.1 General Considerations

All statistical tests will be performed using a two-sided test at a 5% significance level.

If the trial is stopped prematurely due to e.g. futility, the data will be analysed as planned in this statistical analysis plan.

All efficacy endpoints will be analysed for the FAS analysis set, and as a sensitivity the analyses for the primary endpoint will be repeated for the PP population.

Categorical data will be summarised using counts and percentages, while continuous data will be presented using the number of patients (N), mean, standard deviation, median, interquartile range, minimum and maximum. All efficacy endpoints will be listed in patient data listings.

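### The RRT non-inferiority claim is based on a set that keeps patients already on acute RRT at start of IMP, which makes the 20% margin looser for patients who could still start RRT

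*SAP*

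**What the plan says.** SAP section 9.3.1.8 defines the event broadly: "RRT is defined as any form of renal replacement therapy defined as continuous renal replacement therapy, intermittent hemodialysis or peritoneal dialysis". It does not require that RRT begin after IMP. Deaths are added: "all patients dying within the 30-day period will be counted as on RRT".

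The population rule removes chronic cases only: "Patients already on RRT for chronic renal failure at time of inclusion will be excluded from the analysis of incidence of RRT". The claim is then defined on that set. The upper 95% confidence bound for the treatment difference passes if it "is less than 20% of the estimated incidence of RRT in the placebo group".

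The logistic model adjusts for time from shock onset, baseline creatinine, norepinephrine requirement, ventilation and treatment. Acute RRT at baseline is not in it. The section closes with "A subgroup analysis will be performed on patients without acute RRT at baseline" and also plans a forest plot of the non-inferiority tests for all analyses. It does not say that the claim depends on the subgroup, or which result governs if the two disagree.

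**The concern.** The planned subgroup shows that patients on acute RRT at baseline are expected and belong to the main set. Under the event definition such a patient is already a case at time zero, whichever arm he or she is in, so the outcome says nothing about treatment.

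Elsewhere the SAP applies the opposite principle. It drops chronic RRT patients from this same endpoint. In section 9.3.1.6 it does not count organs that had already failed at baseline as new failures.

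Two effects follow, both in the same direction. The certain events raise the placebo incidence, and the margin is a fixed fraction of that incidence, so the margin grows. They also contribute no difference, so an excess among patients who could still start RRT is diluted. Non-inferiority on RRT could then be claimed with a larger at-risk excess than the 20% figure suggests to a reader.

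**Working it through.** **Inputs from the SAP.**
- Non-inferiority is read from the upper limit of a two-sided 95% CI (9.3.1.8), in line with "All statistical tests will be performed using a two-sided test at a 5% significance level" (9.1).
- The margin is 0.2 times the estimated placebo incidence (9.3.1.8).
- The total is 1800 patients (3.2), with one third on placebo in Part 1 and 1:1 in Part 2 (3.1). A Part 1 of 300 gives 200 + 750 = 950 selepressin and 100 + 750 = 850 placebo. A Part 1 of 800 gives 533 + 500 = 1033 and 267 + 500 = 767. A trial that ends with Part 1 at its maximum has 533 and 267.

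**Assumed, because the SAP does not give them.** q, the share on acute RRT at start of IMP, is taken as 1% to 15%. r, the placebo incidence of RRT or death among the remaining patients, is taken as 30% to 40%; section 9.3.2.3 assumes placebo mortality of 20-25%, and deaths count as events here.

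**The plan's own figure.** Section 9.3.1.8 states no rate. The sister rule for mortality (9.3.2.3, margin 30%) gives 2-3% at placebo mortality of 20-25%. Solving d + 1.96*sqrt[(p+d)(1-p-d)/nS + p(1-p)/nP] = 0.3p with 1800 patients gives d = 2.2 points at p = 20% and 3.4 points at p = 25%, for either split. This reproduces the 2-3%, read as the largest passing excess over placebo, so the formula is being used as the SAP intends.

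**Boundary.** Let s be the at-risk incidence on selepressin.
- Placebo, whole set: pP = q + (1-q)r.
- Difference, whole set: (1-q)(s - r).
- At the margin: (1-q)(s - r) = 0.2*[q + (1-q)r], so s - r = 0.2*[r + q/(1-q)].

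This exceeds 0.2r for any q above zero. Example with r = 35%, q = 10%: pP = 0.10 + 0.90*0.35 = 0.415; margin = 0.2*0.415 = 0.083; at-risk excess = 0.083/0.90 = 0.0922; relative to r, 0.0922/0.35 = 26%.

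**Chance of claiming non-inferiority at a true at-risk excess of exactly 20%.** This was simulated with unadjusted proportions and 400,000 trials per setting. Treating the estimated margin as fixed, as the SAP's formula does, inflates the claim rate by itself: it is about 4% at q = 0. To isolate the present point, the table uses the variance of pS - 1.2*pP, which brings q = 0 back to about 2.5%.

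| q | Tolerated at-risk excess, as % of r (r = 40% to 30%) | Claim rate, about 1800 patients | Claim rate, 533/267 |
|---|---|---|---|
| 0 | 20 | 2.5% | about 2.5% |
| 1% | 20.5-20.7 | 3% | 3% |
| 2% | 21.0-21.4 | 3.5% | 3% |
| 5% | 22.6-23.5 | 6% | 4% |
| 10% | 25.6-27.4 | 12% | 7% |
| 15% | 28.8-31.8 | 21% | 10% |

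The claim rates hardly change with r between 30% and 40% or between the two 1800-patient splits. The boundary itself does not depend on sample size.

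**The case against.** The strongest reply is that the SAP has already dealt with this. The subgroup without acute RRT is pre-specified, and the forest plot would probably show its non-inferiority test beside the main one. That makes a discrepancy visible. It does not settle the claim, because the rule is written for the main set only.

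A second reply concerns the estimand, and part of it stands. A reader might infer that the rule breaches a stated 20% limit for at-risk patients. No such limit is stated: the SAP sets 20% of the incidence in the population it analyses, and by that definition a claim at an at-risk excess of 20% is not an error. The claim rates above show how loose the rule is for patients who can still start RRT. They are not breaches of the SAP's own null hypothesis.

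Third, q is unknown. If it is 1-2%, the effect is small.

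Fourth, Appendix 4 takes the incidences from an adjusted logistic model, so the unadjusted identity carries over only approximately.

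Three further inferences are not supported. Under the SAP's fixed-margin formula the claim rates at q = 5, 10 and 15% are about 8%, 16% and 27%, but these also contain the separate margin-variance problem. Superiority does not become easier, since the inclusion only dilutes a difference. Renal safety does not rest on this claim: RRT incidence is outside the Hochberg family in 9.3, and the SAP separately plans renal-failure adverse events, creatinine changes, creatinine clearance and renal SOFA. Nor does the document say anything about dialysis distorting the creatinine covariate.

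**Conclusion.** The concern holds, within limits. Section 9.3.1.8 ties the non-inferiority claim to a set containing patients whose outcome is, by inference from the event definition, fixed before treatment. The margin is therefore looser than 20% for everyone else. The direction follows from algebra. The size depends on q: about 21% of r at 1-2%, rising to 29-32% at 15%, for an assumed r of 30-40% and an unadjusted comparison. It bears on one claim, for one non-key secondary endpoint. It is worth correcting because the remedy is cheap and the rule should not depend on a share that the plan does not state.

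**What to change.** In 9.3.1.8, base the incidence analysis, the 20% margin and the non-inferiority claim on FAS patients who are on no RRT, chronic or acute, at start of IMP. Keep the present set, with only chronic RRT excluded, as a supportive analysis, and state that the restricted set decides the claim. This swaps two analyses that are already planned. RRT status at start of IMP is fixed before treatment, so the restriction does not disturb the randomised comparison. The cost is a change of wording, somewhat fewer patients in the claim, and non-inferiority that is a little harder to show.
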